1. INTRODUCTION

Coronary heart disease is the commonest cause of death worldwide. The World Health Organisation estimates that 3.8 million men and 3.4 million women die from coronary heart disease each year. Since 1990, more people have died from coronary heart disease than any other cause. In the United Kingdom, coronary heart disease is also the single biggest killer. It is responsible for nearly one in six deaths for men and one in ten for women: three times more women die from coronary heart disease than breast cancer. Indeed, 73,000 people die in the United Kingdom every year: one person every 7 minutes. Death rates are particularly high in Scotland, especially in areas of social deprivation. Deaths are sudden and unheralded, increasing the distress of those left behind. Coronary heart disease also has a devastating effect on peoples' lives not just from the large numbers of those who die from it. Disability-adjusted life years, a measure of "healthy years of life lost", can be used to indicate the burden of disease rather than the resulting deaths. The World Health Organisation estimates that coronary heart disease is responsible for 10% of disability-adjusted life years in low-income and 18% in high-income countries. In the United Kingdom, 2.3 million people are living with coronary heart disease [BHF, 2012].

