4.6 Secondary outcomes

The interpretation of trial findings for secondary outcomes will focus on the effect size and 95% CI. No formal adjustment will be made to significance levels to allow for multiplicity.

For each of the following secondary outcomes (appendix C), events are defined as the time to first outcome event during follow-up from date of the index myocardial infarction. Follow-up will be censored at competing causes of death or 15 months from date of MI, whichever occurs first.

Efficacy

- Cardiovascular death and non-fatal myocardial infarction
- Cardiovascular mortality (cardiac and non-cardiac)
- Myocardial infarction (fatal and non-fatal)
- Stent thrombosis
- Coronary revascularisation
- Thrombotic stroke

Safety

- Non-cardiovascular death (including fatal bleeding) and major non-fatal bleeding
- Non-cardiovascular death (including fatal bleeding)
- Major fatal and non-fatal bleeding
- Hospitalisation for bleeding
- Intracranial haemorrhage
- Gastrointestinal bleeding

The analysis will follow that specified for the primary outcome in section 4.5. The number and proportions of participants with an event for individual components of the secondary outcomes will also be reported alongside the composite.

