4.6.1 Sensitivity analyses

Competing risk of death

To take into account the possibility of a competing risk of death, a Fine and Gray[3] proportional sub-distribution hazards regression model will be used to take into account the competing risk of death to provide reassurance about the robustness of the analysis. The effect of the randomised intervention will be presented by the sub-distribution hazard ratio and 95% confidence interval. The cumulative incidence function (CIF) obtained from the Fine-Gray model will be plotted separately for each intervention; the median time to event and its 95% CI will be reported by intervention group. The absolute risk difference (and its 95% CI) will also be reported at the median time to event.

Diagnostic position

The analysis of secondary safety outcomes, will consider the occurrence of an event if the diagnostic codes, as defined in Appendix C, occur in any diagnostic position.

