Appendix C

Outcomes defined used the following codes and positions specified below following the date of index MI unless otherwise specified. If the code is not identified in any admissions/deaths then they will be assumed to not have the outcome of interest.

Data sources

Scotland: SMR00 / SMR01 / NRS Deaths / Prescribing Information System / Scottish Blood Transfusion Database

England: Hospital Episode Statistics / Civil Registrations of Death / Medicines dispensed in Primary Care (NHSBSA data)

Outcome	Code (ICD-10 , OPCS4)
All-cause mortality	Any record of death.
Non-cardiovascular death (including fatal bleeding) and major non-fatal bleeding	
Death due to a non-cardiovascular cause
 
Primary position for cause of death
 
Ax, Bx, Cx, Dx Ex, Fx , Gx , Hx , Jx, Kx , Lx , Mx , Nx , Ox , Px , Qx , Rx , Sx , Tx , Ux , Vx , Xx , Yx , Zx.
 
OR
 
Hospitalisation for bleeding
 
Primary or first secondary position
 
I60x, I61x, I62x, S06.4x, S06.5x, S06.6x, K92.0x, K92.1x, K 92.2x, I85.0x, I98.3x, K22.6x, K25.0x, K25.2x, K25.4x, K25.6x, K26.0x, K26.2x, K26.4x, K26.6x, K27.0x, K27.2x, K27.4x, K27.6x, K28.0x, K28.2x, K28.4x, K28.6x, K29.0x, K62.5x, K66.1x, R58x, I23.0x, I31.2x, I69.0x, I69.1x, I69.2x, H21x, H35.6x, H31.3x, H43.1x, H44.8x, H45.0x, R04.0x, R04.1x, R04.2x, R04.8x, R04.9x, T81.0x, D62x, N83.7x, N93.8x , N93.9x, O03.1x, O03.6x, O04.1x, O04.6x, O05.1x, O05.6x, O06.1x, O06.6x, O20.8x, O20.9x, O46x , O67x, O07.1x, O07.6x, O08.1x, O71.7x , O72.0x , O72.1x , O72.2x , O90.2x , P26.1x , R31x , M25.0x.
 
OR

	
Primary procedure position (OPSC4)
 
E05x , E058x , E059x , F162x , D041x , E203x , F365x , G523x , H212x , H531x , K681x , P093x , P271x , T301x , Y221x , T032x , Y221x , T032x , Y321x , V032x , A052x , A053x , A054x , A103x , A401x , A411x

Non-cardiovascular death (including fatal bleeding)	
Primary cause of death
 
Ax , Bx , Cx , Dx , Ex , Fx , Gx , Hx , Jx , Kx , Lx , Mx , Nx , Ox , Px , Qx , Rx , Sx , Tx , Ux , Vx , Xx , Yx , Zx

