Hospitalisation for bleeding	
Hospitalisation for bleeding
 
Primary or first secondary position
 
I60x, I61x, I62x, S06.4x, S06.5x, S06.6x, K92.0x, K92.1x, K 92.2x, I85.0x, I98.3x, K22.6x, K25.0x, K25.2x, K25.4x, K25.6x, K26.0x, K26.2x, K26.4x, K26.6x, K27.0x, K27.2x, K27.4x, K27.6x, K28.0x, K28.2x, K28.4x, K28.6x, K29.0x, K62.5x, K66.1x, R58x, I23.0x, I31.2x, I69.0x, I69.1x, I69.2x, H21x, H35.6x, H31.3x, H43.1x, H44.8x, H45.0x, R04.0x, R04.1x, R04.2x, R04.8x, R04.9x, T81.0x, D62x, N83.7x, N93.8x , N93.9x, O03.1x, O03.6x, O04.1x, O04.6x, O05.1x, O05.6x, O06.1x, O06.6x, O20.8x, O20.9x, O46x , O67x, O07.1x, O07.6x, O08.1x, O71.7x , O72.0x , O72.1x , O72.2x , O90.2x , P26.1x , R31x , M25.0x.
 
OR
 
Primary procedure position (OPCS4)
 
E05x , E058x , E059x , F162x , D041x , E203x , F365x , G523x , H212x , H531x , K681x , P093x , P271x , T301x , Y221x , T032x , Y221x , T032x , Y321x , V032x , A052x , A053x , A054x , A103x , A401x , A411x

Intracranial haemorrhage	
Intracranial haemorrhage event
 
Primary or first secondary position
 
I60x , I61x , I62x , S06.5x , S06.6x.

	
OR
 
Death due to intracranial haemorrhage
 
Primary cause of death
 
I60x , I61x , I62x , S06.5x , S06.6x.

Gastrointestinal bleeding	
Gastrointestinal bleeding event
 
Primary or first secondary position
 
K92.0x , K92.1x , K 92.2x , I85.0x , I98.3x , K22.6x , K25.0x , K25.2x , K25.4x , K25.6x , K26.0x , K26.2x , K26.4x , K26.6x , K27.0x , K27.2x , K27.4x , K27.6x , K28.0x , K28.2x , K28.4x , K28.6x , K29.0x , K62.5x , K55.2x , K66.1x.
 
OR
 
Death due to Gastrointestinal bleeding
 
Primary cause of death
 
K92.0x , K92.1x , K 92.2x , I85.0x , I98.3x , K22.6x , K25.0x , K25.2x , K25.4x , K25.6x , K26.0x , K26.2x , K26.4x , K26.6x , K27.0x , K27.2x , K27.4x , K27.6x , K28.0x , K28.2x , K28.4x , K28.6x , K29.0x , K62.5x , K55.2x , K66.1x.

Cardiovascular mortality and non-fatal myocardial infarction	
Death due to a cardiovascular cause
 
Primary cause of death
 
Ix
 
OR
 
Myocardial infarction after the Index Admission Discharge Date

	
Primary or first secondary position
 
I21x, I22x

Cardiovascular mortality (cardiac and non-cardiac)	
Death due to a cardiovascular cause
 
Primary cause of death
 
Ix

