Myocardial infarction (fatal and non- fatal)	
Myocardial infarction after the Index Admission Discharge Date
 
Primary or first secondary position
 
I21x, I22x
 
OR
 
Death due to myocardial infarction
 
Primary cause of death
 
I21x, I22x

Stent thrombosis	
Stent thrombosis
 
Primary or first secondary position
 
T82.8x

Coronary revascularisation	
Coronary revascularisation after the Index Admission Discharge Date
 
Primary procedure position (OPCS4)

	K40x, K41x, K42x, K43x, K44x, K45x, K46x, K47x, K48x, K49x, K50x, K75x.
Thrombotic stroke	
Ischaemic stroke
 
Primary or first secondary position
 
I63x
 
OR
 
Death due to ischaemic stroke
 
Primary cause of death
 
I63x

Blood transfusion	Any record of transfusion
Iron therapy	
Prescribed Iron Therapy
 
Approved drug names: FERROUS SULPHATE, FERROUS FUMARATE, FERROUS GLUCONATE, FERRIC MALTOL, FERROUS CALCIUM CITRATE, FERROUS GLYCINE SULFATE, IRON CARBOXYMALTOSE, SODIUM FEREDETATE, IRON CARBOXYMALTOSE, IRON DEXTRAN, IRON SUCROSE, VENOFER, FERINJECT

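### Appendix C counts deaths of ill-defined or unknown cause (ICD-10 R95-R99) as non-cardiovascular safety deaths, and no planned analysis tests that choice

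*SAP*

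**What the plan says.** SAP Appendix C has two rows that use non-cardiovascular death: the outcome on its own, and its composite with major non-fatal bleeding, where the component is labelled "Death due to a non-cardiovascular cause". Both rows list the same ICD-10 chapters in the primary cause-of-death position. The list includes "Ox , Px , Qx , Rx , Sx , Tx , Ux", so all of chapter R is in.

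On the efficacy side, "Death due to a cardiovascular cause" means a primary cause in chapter I and nothing else. "Death due to myocardial infarction" means I21 or I22 only.

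Appendix C has no category for an undetermined cause. Its default is "If the code is not identified in any admissions/deaths then they will be assumed to not have the outcome of interest". SAP 4.6 adds: "Follow-up will be censored at competing causes of death or 15 months from date of MI, whichever occurs first".

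SAP 4.6.1 offers two sensitivity analyses for the secondary outcomes. One is a Fine and Gray model. The other applies to the safety outcomes only, and accepts a listed code wherever it stands in the record. Neither document describes adjudication of cause of death.

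**The concern.** The SAP uses ICD-10, in which R95-R99 is the block for ill-defined and unknown causes of death. That meaning belongs to the classification; the SAP does not spell it out. A death certified this way gives no evidence that the cause was non-cardiovascular. In patients who have just had a myocardial infarction, some of these deaths may be cardiac.

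The direction matters because the trial weighs ischaemic harm from stopping early against bleeding harm from continuing (protocol 2 and 11.6). Protocol 1.1 itself expects a short period of rebound stent thrombosis and infarction after the switch to single therapy. If some unexplained deaths in the 3-month arm were ischaemic, the rule would score them as safety events in that arm and leave them out of cardiovascular death. If they were unrelated to treatment, they would dilute the non-cardiovascular contrast. A reader could not tell which had happened, because the plan never shows these deaths separately.

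Non-cardiovascular mortality is not a peripheral outcome. Protocol 9.2 gives it its own power statement, and protocol 9.3 names it for cause-specific analysis.

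**Working it through.** **1. Where each death goes under Appendix C and SAP 4.6**

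| Primary cause of death | Non-cardiovascular death | Cardiovascular death | Fatal MI component |
|---|---|---|---|
| I21, I22 | censored | event | event |
| Other I code | censored | event | censored |
| R95-R99 | event | censored | censored |
| R04 (listed subcodes), R31, R58 | event (also a bleeding death) | censored | censored |
| W code | in neither list | in neither list | not an event |

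An R95-R99 death also counts in the composite of non-cardiovascular death and major bleeding. It does not count in the composite of cardiovascular death and non-fatal infarction, although an infarction recorded earlier already counts there. The Fine and Gray model changes how competing deaths are handled, not which class a death belongs to. The any-position analysis widens the safety definitions, so it cannot take an R-coded death out of them.

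**2. The plan's own figure for this outcome**

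Protocol 9.2 states 81% power for 6% against 5% non-cardiovascular mortality with 8,472 per group, two-sided 0.05. With pooled variance and no continuity correction:

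z = [0.01 × √8472 − 1.96 × √(2 × 0.055 × 0.945)] / √(0.06 × 0.94 + 0.05 × 0.95) = (0.920 − 0.632) / 0.322 = 0.895, which gives 81.5%.

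The stated figure reproduces. At the 4,576 patients recruited in the UK (2,288 per group) the same formula gives 32%.

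**3. Share of counted non-cardiovascular deaths**

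Inputs from protocol Table 2, Scotland, one year: 25.4% all-cause, 17.8% cardiovascular and 7.6% non-cardiovascular mortality. Since 17.8 + 7.6 = 25.4, the 7.6% is a share of patients, not of deaths. The R95-R99 share s of all deaths is in neither document; 1% to 5% is assumed. The calculation also assumes that the 7.6% already includes these deaths.

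x = s × 25.4 / 7.6

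- s = 1%: x = 3.3%
- s = 2%: x = 6.7%
- s = 5%: x = 16.7%

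Relative to cardiovascular deaths the same counts are s × 25.4 / 17.8, or 1.4% to 7.1%.

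**4. Effect on the hazard ratio**

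Take 0.83 as the ratio for the remaining non-cardiovascular deaths (protocol 9.2 quotes it for non-cardiac mortality). Treat the counted ratio as a weighted average, with ratio r in the R95-R99 deaths: 0.83 × (1 − x) + r × x.

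- No effect (r = 1.0): 0.836, 0.841, 0.858
- Illustrative ischaemic excess with 3 months (r = 1.2, assumed): 0.842, 0.855, 0.892

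**5. Against the precision available**

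Reduce the Scottish rates by one third, as protocol 9.2 does, and apply them to the 4,576 UK patients.

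- Non-cardiovascular deaths: 4,576 × 0.076 × 0.667 = 232
- All deaths: 4,576 × 0.254 × 0.667 = 775, so 1% to 5% is about 8 to 39 deaths
- SE(log HR) ≈ √(4/232) = 0.131
- 95% interval around 0.83: exp(−0.186 ± 1.96 × 0.131) = 0.64 to 1.07

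These are one-year rates, while follow-up is 15 months, and international patients are left out. The counts are therefore only a guide.

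**The case against.** The strongest reply is that a two-way split by chapter is a stated, reproducible rule applied alike to both arms, and that the main conclusion does not depend on it. All-cause mortality was chosen as primary because it captures the trade-off in one outcome, and Appendix C takes any record of death. SAP 4.6 also says that secondary outcomes will be read through effect sizes and confidence intervals. A neutral shift of at most 0.03 in the hazard ratio is small beside an interval of roughly 0.64 to 1.07. All of this stands, and it is why the point is minor.

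Three stronger readings are tempting, and the documents do not support them.

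- A reader might infer that every R-coded death is of unknown cause, so that all of chapter R should move. The SAP itself lists R04, R31 and R58 among the codes for death due to bleeding. Moving them would take bleeding deaths out of an outcome labelled as including fatal bleeding.
- A reader might infer that sudden deaths after infarction in general vanish from the efficacy outcomes. Any sudden death certified under an I code still counts as cardiovascular. The protocol's remark that "Deaths are sudden and unheralded, increasing the distress of those left behind" is introductory epidemiology about coronary disease, and says nothing about deaths certified without a cause.
- A reader might infer that these deaths are known to be in the wrong class. Their cause is unknown, so the defect is that the allocation is untested, not that it is shown to be false.

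The reply does not answer one thing: a difference between arms in these deaths would move events from one side of the trial's central comparison to the other, and no planned table or analysis would show it.

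**Conclusion.** The point holds in a narrow form. Deaths with primary cause R95-R99 are always counted as non-cardiovascular safety deaths and censored from cardiovascular death, and nothing in the plan tests this. It touches only cardiovascular death, non-cardiovascular death, their two composites and, through censoring, the infarction outcome.

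The size is unknown. Under the assumed 1% to 5% of all deaths, these would be about 3% to 17% of counted non-cardiovascular deaths. A hazard ratio of 0.83 would move to about 0.84 to 0.86 if treatment had no effect in them, and further if they included an ischaemic excess with 3 months. Both results rest on the Table 2 rates and an assumed share, so they illustrate and do not estimate. No bias in the primary result follows from any of this.

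**What to change.** In Appendix C, identify deaths with primary cause R95-R99 as undetermined cause and tabulate them by arm. They remain in all-cause mortality. Leave R04, R31, R58 and all other R codes in non-cardiovascular death. The main definitions in the finalised SAP need not be rewritten.

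In SAP 4.6.1, add one sensitivity analysis of four outcomes: cardiovascular death, non-cardiovascular death, cardiovascular death with non-fatal infarction, and non-cardiovascular death with major non-fatal bleeding. In it, count the undetermined deaths as cardiovascular instead of non-cardiovascular.

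The cost is one table row and one extra analysis run on data already held. If the count is trivial, the table will show it and the matter is closed.

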7 STUDY ASSESSMENTS

7.1 DATA COLLECTION AND OUTCOME ASSESSMENTS

Baseline patient characteristics, past medical history and medication use will be obtained from the randomisation database and data linkage from the participant's electronic health records.

Outcome measures for patients recruited in Scotland will be obtained through the Farr Institute in collaboration with the electronic Data Research and Innovation Service (eDRIS) and the General Register Office as we have successfully achieved with the SCOT-HEART [SCOT-HEART, 2015; Williams et al, 2016] and HighSTEACS [Shah et al, 2015a; Shah et al, 2015b] trials (Tables 2 and 3). We will capture all hospital admission events and will have access to clinical records and imaging as required through NHS Safe Havens. Outcome measures for patients recruited in England will be obtained through NHS Digital. We will record the following safety endpoints: all-cause death, non-cardiovascular death, fatal bleeding, major bleeding (including gastrointestinal and intracranial haemorrhage), hospitalization for bleeding (all ICD-10 coded), as well as blood transfusions, where possible). The bleeding data will be used to classify bleeding events using the standardized bleeding definition for cardiovascular clinical trials as defined by the Bleeding Academic Research Consortium (BARC) [Mehran et al, 2011]. We will record the following efficacy endpoints: all-cause death, cardiovascular (cardiac and non-cardiac) death, myocardial infarction (non-fatal and fatal) [Thygesen et al, 2012], stroke (non-fatal and fatal; thrombotic and haemorrhagic), coronary revascularisation (percutaneous coronary intervention and coronary artery bypass graft surgery), and stent thrombosis.

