4.9 Extended follow-up

The analyses of the primary and secondary outcomes will be repeated censoring at the date of last available follow-up.

⁴ The Haemoglobin outcome in the protocol will not be analysed, as the data is not nationally linked.

5. Validation and QC

The following will be done by a second statistician:

1. The code will be checked and run to ensure results are as stated
2. Check of data fidelity from raw data to SAS data files (random selection)
3. Check treatment allocation consistent between UK and NZ datasets
4. Check of ICD10/OPCS4 (or equivalents codes) in SMR01 (or equivalent datasets) map to the study SAP
5. The statistical report will be read and sense-checked.

6. Data sharing

Data will be stored inside a Trusted Research Environment (TRE) managed by AIMES on behalf of ECTU for 12 years. Access to the data needs to be approved, there are no data sharing agreements, protocols or contracts in place or planned.

7. References

1. Royston, P. and M.K. Parmar, *The use of restricted mean survival time to estimate the treatment effect in randomized clinical trials when the proportional hazards assumption is in doubt*. Stat Med, 2011. **30**(19): p. 2409-21.
2. Burke, D.L., J. Ensor, and R.D. Riley, *Meta-analysis using individual participant data: one-stage and two-stage approaches, and why they may differ*. Statistics in Medicine, 2017. **36**(5): p. 855-875.
<https://doi.org/10.2307/2670170>

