Major fatal and non-fatal bleeding	
Hospitalisation for bleeding
 
Primary or first secondary position
 
I60x, I61x, I62x, S06.4x, S06.5x, S06.6x, K92.0x, K92.1x, K 92.2x, I85.0x, I98.3x, K22.6x, K25.0x, K25.2x, K25.4x, K25.6x, K26.0x, K26.2x, K26.4x, K26.6x, K27.0x, K27.2x, K27.4x, K27.6x, K28.0x, K28.2x, K28.4x, K28.6x, K29.0x, K62.5x, K66.1x, R58x, I23.0x, I31.2x, I69.0x, I69.1x, I69.2x, H21x, H35.6x, H31.3x, H43.1x, H44.8x, H45.0x, R04.0x, R04.1x, R04.2x, R04.8x, R04.9x, T81.0x, D62x, N83.7x, N93.8x , N93.9x, O03.1x, O03.6x, O04.1x, O04.6x, O05.1x, O05.6x, O06.1x, O06.6x, O20.8x, O20.9x, O46x , O67x, O07.1x, O07.6x, O08.1x, O71.7x , O72.0x , O72.1x , O72.2x , O90.2x , P26.1x , R31x , M25.0x.
 
OR
 
Primary procedure position (OPCS4)
 
E05x , E058x , E059x , F162x , D041x , E203x , F365x , G523x , H212x , H531x , K681x , P093x , P271x , T301x , Y221x , T032x , Y221x , T032x , Y321x , V032x , A052x , A053x , A054x , A103x , A401x , A411x
 
OR
 
Death due to bleeding
 
Primary cause of death

	I60x, I61x, I62x, S06.4x, S06.5x, S06.6x, K92.0x, K92.1x, K 92.2x, I85.0x, I98.3x, K22.6x, K25.0x, K25.2x, K25.4x, K25.6x, K26.0x, K26.2x, K26.4x, K26.6x, K27.0x, K27.2x, K27.4x, K27.6x, K28.0x, K28.2x, K28.4x, K28.6x, K29.0x, K62.5x, K66.1x, R58x, I23.0x, I31.2x, I69.0x, I69.1x, I69.2x, H21x, H35.6x, H31.3x, H43.1x, H44.8x, H45.0x, R04.0x, R04.1x, R04.2x, R04.8x, R04.9x, T81.0x, D62x, N83.7x, N93.8x , N93.9x, O03.1x, O03.6x, O04.1x, O04.6x, O05.1x, O05.6x, O06.1x, O06.6x, O20.8x, O20.9x, O46x , O67x, O07.1x, O07.6x, O08.1x, O71.7x , O72.0x , O72.1x , O72.2x , O90.2x , P26.1x , R31x , M25.0x.

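### The SAP's major bleeding outcome has no severity test: its non-fatal part is coded identically to hospitalisation for bleeding, and the BARC classification is dropped without comment

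*SAP*

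**What the plan says.** Protocol Table 3 and SAP 4.6 each list "Major fatal and non-fatal bleeding" and hospitalisation for bleeding as separate secondary safety outcomes. Both also list a composite, "Non-cardiovascular death (including fatal bleeding) and major non-fatal bleeding".

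Protocol 7.1 says of severity: "The bleeding data will be used to classify bleeding events using the standardized bleeding definition for cardiovascular clinical trials", naming BARC as the source of that definition. It also foresees blood transfusion data where obtainable and access to clinical records.

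SAP Appendix C turns these outcomes into codes. The admission limb of major bleeding sits under a sub-heading that is itself hospitalisation for bleeding. Its diagnosis list opens "I60x, I61x, I62x, S06.4x, S06.5x, S06.6x, K92.0x, K92.1x, K 92.2x, I85.0x" and later includes "R04.0x, R04.1x, R04.2x, R04.8x, R04.9x, T81.0x, D62x, N83.7x, N93.8x". The rule for where a diagnosis must appear is "Primary or first secondary position". A list of OPCS4 procedures in primary position also qualifies.

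On possible severity data, SAP footnote 4 says: "The Haemoglobin outcome in the protocol will not be analysed, as the data is not nationally linked". SAP 4.7 keeps blood transfusion only as a stand-alone descriptive outcome.

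**The concern.** If a protocol names major bleeding and hospitalised bleeding as two outcomes and promises a bleeding classification, a reader will assume that something in the data separates them. In Appendix C nothing does so for non-fatal events.

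The trade-off between bleeding and atherothrombotic events is the stated rationale of the trial (Protocol 1.8 and 11.6), so the major bleeding result will be read closely. SAP 4.6 says secondary outcomes will be interpreted through effect size and confidence interval, so the label attached to that effect size carries weight. Two things are at stake:

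- A hazard ratio published as major bleeding would describe fatal or hospitalised bleeding of any severity. The same applies to the non-fatal bleeding limb of the first safety composite.
- Two safety outcomes would agree because they count largely the same events, and that agreement could be mistaken for confirmation.

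**Working it through.** The plan states no figure for this outcome, so the check compares definitions.

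**Step 1: the Appendix C lists.** Spaces and dots were removed and the lists compared as sets.

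| Element | Composite, bleeding limb | Major bleeding, admission limb | Hospitalisation for bleeding |
|---|---|---|---|
| ICD-10 entries | 76 | 76 | 76 |
| Position | primary or first secondary | primary or first secondary | primary or first secondary |
| OPCS4 entries, primary procedure | 26 (24 distinct) | 26 (24 distinct) | 26 (24 distinct) |

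No entry appears in one list and not in the others, for diagnoses or procedures. The 26 against 24 arises because Y221x and T032x are each listed twice in all three places.

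**Step 2: what major bleeding adds.** It adds one limb: death with a listed code as primary cause. That limb uses the same 76 entries. Hence

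- major bleeding = hospitalisation for bleeding, plus bleeding deaths with no earlier qualifying admission;
- non-fatal major bleeding = hospitalisation for bleeding, with no remainder.

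This conclusion does not depend on the clinical meaning of any code.

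**Step 3: how large the added limb might be.** The only inputs are planning rates in Protocol 9.2: 0.92% fatal bleeding at one year in unselected patients, with risk one-third lower in consenting patients.

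- Both arms at that rate: 0.0092 × 2/3 = 0.0061; 0.0061 × 4,576 = 28 deaths.
- On the protocol's planned contrast of 0.6% and 0.3%, with equal arms of 4,576 / 2 = 2,288: 2,288 × 0.006 + 2,288 × 0.003 = 13.7 + 6.9 = 20.6, about 21 deaths.

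Deaths preceded by a qualifying admission add nothing, which lowers the count. Follow-up to 15 months and the New Zealand participants raise it. The figures give an order of magnitude only. The documents give no expected number of bleeding admissions, so the overlap cannot be turned into a percentage.

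**Step 4: whether severity enters elsewhere.**

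- BARC: not used in any analysis section or appendix of the SAP text available.
- Haemoglobin: not analysed (footnote 4).
- Transfusion: descriptive only (SAP 4.7), not part of any bleeding definition.
- Sensitivity analysis (SAP 4.6.1): accepts the codes in any diagnostic position, which broadens the definition and adds no severity test.

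**Step 5: whether the departure is declared.** SAP footnotes 1, 3 and 4 explain the handling of the small treatment groups, the removal of centre from the primary model, and the loss of haemoglobin. None mentions BARC.

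**Side finding.** K55.2x is in the gastrointestinal bleeding list but not in the 76-entry list, so such an admission could count as a gastrointestinal bleed without counting as a major or hospitalised bleed.

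**The case against.** Hospitalised bleeding is a legitimate pragmatic outcome for a record-linkage trial, and Protocol 7.1 describes the bleeding endpoints as ICD-10 coded. The protocol never sets a BARC grade as the threshold for major bleeding, so it would be wrong to infer that a BARC-defined endpoint has been replaced. This stands. It narrows the criticism to a label without content and a promised classification dropped without explanation.

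The definition is also not fully permissive. A diagnosis must be in primary or first secondary position and a procedure in primary position, so not every coded bleeding admission counts. This stands too, but hospitalisation for bleeding has the same restrictions, so they do not separate the two outcomes.

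A reader might infer that the plan has no measure of serious non-fatal bleeding. The documents do not support that: intracranial haemorrhage and gastrointestinal bleeding are separate outcomes with their own code lists, and SAP 4.6 reports the components of composites. A reader might also infer that the trial's main answer is compromised. It is not: the principal question is the default duration of therapy, judged on all-cause mortality, which Appendix C defines as any record of death.

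**Conclusion.** Wrong as written, at the level of a secondary safety outcome and one limb of a secondary composite. Following the SAP exactly yields a major bleeding result with no severity condition on non-fatal events and a near-duplicate outcome beside it. The identity of the code lists is a matter of direct comparison and rests on no assumption.

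The numerical consequence is not known. A reader might infer that the major bleeding rate is inflated by some definite factor, or that its hazard ratio is diluted towards 1. A stricter subset of these events could not have a higher rate, but the size of the gap needs the fraction of coded admissions that are truly major, which the documents do not give. Nor do they support a claim of dilution. The hazard ratio of 0.58 in Protocol 9.2 is for bleeding without a severity qualifier. If it held for major and other bleeds alike, with f the fraction that are major, the blend would be approximately f × 0.58 + (1 − f) × 0.58 = 0.58 for any f, that is, no dilution. Protocol 1.6 attributes both minor and major bleeding to the therapy, which gives no reason to assume a null effect on the less severe events.

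**What to change.** In SAP 4.6 and Appendix C:

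1. Rename the outcome fatal or hospitalised bleeding, and rename the composite limb to match.
2. Add a footnote that the BARC classification in Protocol 7.1 is not applied, with the reason. If the reason is that haemoglobin is not nationally linked, say so.
3. State that this outcome and hospitalisation for bleeding overlap almost fully and are not independent evidence.

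These steps change wording only. They need no new data and leave every planned model as it is.

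Optionally, add a supportive analysis of a stricter definition: bleeding as primary cause of death, intracranial haemorrhage, or a bleeding admission with a linked transfusion record. Appendix C names a transfusion database for Scotland only, so this analysis should be confined to Scotland, which SAP 4.5.2 says supplies most participants. It should not be pooled with countries that have no transfusion data, because the outcome would then mean different things by country. Appendix C accepts any record of transfusion, so a rule tying the transfusion to the bleeding admission would have to be written first. The price is few events and wide intervals, in a trial whose protocol already expects limited numbers of events.
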